4.1.1 Primary outcome

• Superiority of valproate compared to placebo on the Positive and Negative Syndrome Scale (PANSS) positive subscale at the 12-month visit [4].

The primary outcome is the positive subscale of the PANSS, which measures psychotic symptom severity. The PANSS is a clinician-rated scale that assesses psychotic (positive), negative and general symptom severity in schizophrenia. The PANSS psychotic (positive) rating at the end of the double-blind study (12 months) will serve as the main outcome measure [4]. The positive scale has seven items covering psychotic symptoms (delusions, conceptual disorganization, hallucinations, excitement, grandiosity, suspiciousness/persecution and hostility), each rated from 1 (absent) to 7 (very severe). The scale's reliability, criterion-related validity, and construct validity have been well documented [29].

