4.2 Trial Design

This multi-site study will use a two-arm, randomized, double blinded, placebo-controlled trial using an intention to treat analysis (ITT). Patients with a diagnosis of schizophrenia or schizoaffective disorder on an antipsychotic (non-clozapine) for at least 6 weeks, continuing to have positive psychotic symptoms, will be randomised 1:1 to either placebo + continuing antipsychotic treatment arm or valproate + continuing antipsychotic treatment arm (Flow diagram). Randomisation will be stratified by sex, diagnostic category (schizophrenia or schizoaffective) and site and both in-patient as well as outpatients will be eligible to participate.

Patients must be on one or more non-clozapine oral antipsychotic for at least 6 weeks and should be on a stable dose for at least 2 weeks preceding the screening visit. In case of depot the dose must be stable for at least 2 treatment cycles or at least 30 days (whichever is longer) prior to the screening visit. During the trial, clinicians will also be able to adjust the antipsychotic dose, change formulation, change antipsychotics or even add if needed as this is a pragmatic trial. The addition or change of antipsychotic to clozapine will however be considered as discontinuation of the intervention and patients will be withdrawn from the study medication after down titrating their treatment. All subjects will receive follow-up assessments, including those who discontinue the study medication.

The trial will include a titration phase for the study medication lasting for approximately 2 weeks followed by a maintenance phase for the remaining 50 weeks of the study. At the end of the 52-week treatment period, subjects will be down titrated over 2 weeks. Outcomes will be measured at 3, 6 and 12 months using standard rating scales and after patients have finished the medication phase, follow up study indices will be obtained using electronic health records till the end of the study.

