Flow Diagram Patients to be assessed post consent (N = 460)Diagnosis of schizophrenia and schizoaffective (DSM-5) Inadequate response to first line antipsychotics Fail to meet inclusion criteria (symptom severity, comorbid conditions, past medication adherence history, clinical safety criteria) Withdrawal of consent Baseline assessment (N = 362) Including PANSS '+'ive score Randomization 1:1 allocation (Time point 0) Placebo + current antipsychotic (N = 181) Valproate + current antipsychotic (N = 181) 3 and 6 month follow up 3 and 6 month follow up Primary outcome (PANSS '+'ive score) Primary outcome (PANSS '+'ive score) Secondary outcomes Secondary outcomes Double blind phase Pharmacoeconomic measures Pharmacoeconomic measures One year follow up (N = ~145) One year follow up $(N = \sim 145)$ Outcomes similar to earlier time point Outcomes similar to earlier time point Attrition 10-20% from baseline Attrition 10-20% from baseline Mainly due to withdrawal of consent Mainly due to withdrawal of consent Post-one year follow up Post-one year follow up Annual electronic records Annual electronic records HoNOS database HoNOS database Electronic patient journey records Electronic patient journey records

Attrition rate of 30% at the randomization step and 20% from allocation based on two similar augmentation studies – Morrison et al, Lancet Psychiatry, 2018. Vol 5:p663 and Cipriani et al, J Clin Psychopharmacology, 2013. Vol 33(4):p533.

DSM-5 - Diagnostic and Statistical Manual of Mental Disorders, Fifth Edition (Standard manual for psychiatric diagnosis); PANSS - Positive and Negative Syndrome Scale (Clinical scale for evaluating severity of schizophrenia); HoNOS - Health of the Nation Outcome Scales (a measure of the health and social functioning in psychiatric patients captured yearly by mental health care teams)

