4.3 Trial Flowchart

The study will consist of three periods. Screening, a treatment period and a long-term follow-up period. The schematic of the first two periods are shown in Figure 1. The Trial Schedule (Table 1) at the end of this section gives a snap shot of all clinical assessments that will be performed.

Figure 1: Study Schematic

Study visit V3, can take place + / - 3 days from the specified week while study visits V4, V5 and V6 can take place within +/- 2 weeks of the specified week. The same apply to the respective dispensing visits. At the end of the 12-month period, down-titration will take place over approximately two weeks depending on the maintenance dose in steps of 500mg in 3-4 day intervals. V7 is the follow up visit after valproate/placebo has been completely stopped and can take place within one week after the last consumed study drug. Assessments will be conducted as closely as possible to the timeframe mentioned however if a major variation arises, it will be factored in the analysis. A single follow up via telephone or face-to-face, 60 days since their last study drug intake will also be conducted to record for any AEs/SAEs

Screening period (approximately – 8 to 0 weeks)

Clinical teams will first alert suitable patients to the study. If the patients are interested in being contacted by the research team, then the research team will get in touch with them. If patients have already given consent to be contacted for research (for example through a consent-to-consent procedure), then the study team will make contact directly and if the patient consents then the patient's clinical care provider will be informed of their participation. Patients will also be allowed to contact the study team via adverts displayed in waiting rooms, and relevant media (e.g. patient newsletters). When contacted or if the study team has permission to contact the patient then a member from the study team will have a face to face conversation or via the telephone to give the patient more details about the study. If the patient is interested in participating in the study, they will then be invited for consenting and screening where

further details of the study will be discussed and the informed consent form (ICF) of the study will be presented.

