6.5 Withdrawal of Subjects

Participants have the right to withdraw from the study at any time for any reason. The investigator also has the right to withdraw patients from the study drug in the event of inter-current illness, AEs, SAE's, SUSAR's, protocol violations, cure, administrative reasons or other reasons. SAE's and SUSAR's will be followed up until resolution and outcomes will be recorded for the DMEC and TSC to review. It is understood by all concerned that an excessive rate of withdrawals can render the study un-interpretable; therefore, unnecessary withdrawal of patients should be avoided. In the event of hospitalization of patients unrelated to the study drug, patients will be reviewed for their continuation in the study and, if needed, will be recommended for a drug holiday as described in the next paragraph. Should a patient decide to withdraw from the study, the reason for withdrawal will be recorded in the exit interview if they provide us with one. Should a patient discontinue from study drug only, efforts will be made to continue to obtain follow-up data, with the permission of the patient.

Poor compliance (no minimum threshold) will not merit withdrawal but will be recorded and follow-up data will be continued to be obtained. Study drug holiday is permissible in case of an emergency, or for elective surgery or medical procedures. The process for the drug holiday is that when subjects will undergo a down titration till IMP is completely stopped as described in Section 4.3 and will then be up titrated when they re-join the

study. In such cases their assessments will be delayed depending on the study drug holiday period.

6.6 Expected Duration of Trial.

The total duration of the trial is expected to be 5 years. The end of the trial will be defined as last patient to complete visit 7 (V7), including the 60-day follow-up period to assess AE/SAEs after the last day of medication. Each individual subject will remain on the active trial for 12 months, +/- two weeks for the discontinuation of the treatment at the end. Long-term annual follow-up using clinical and electronic records will be conducted up to the point where the last patient completes Visit 7 for the entire trial.

7 Trial Procedures

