- If an increase in dose is executed at this visit then a telephone call to check on tolerability to be conducted after three days

Visit 5 & DS4: 6-month visit (week 26)

- Obtain medical and medication history since last visit
- Conduct Medication Adherence Rating Scale (for antipsychotic medication)

- Risk assessment using the Columbia Suicide Severity Rating scale
- Conduct clinical interviews (PANSS, CGI-SCH, CDSS, YMRS, MOAS, SWEMBS, SF-36, CSRI, UKU)
- Record height and weight
- Record vital signs (blood pressure/pulse rate)
- Remind female participants to continue to use effective long-term methods of contraception during the study
- If there is a gap in contraception or if the contraceptive method has been changed then conduct a urine pregnancy test before dispensing study medication
- Conduct a pill count of the IMP
- Dispense 3 months of medication (check if completed annual risk acknowledgment form for female subjects of childbearing potential remains valid at this time-point but also if it lasts till the end of medication phase and if needed perform a serum pregnancy test and complete a fresh annual risk acknowledgement form)

DS 5: 9-month dispensing session (week 36)

- Remind female participants to continue to use effective long-term methods of contraception during the study
- If there is a gap in contraception or if the contraceptive method has been changed then conduct a urine pregnancy test before dispensing study medication
- Conduct a pill count of the IMP
- Dispense 3 months of medication (check if annual risk acknowledgment form for female subjects of childbearing potential remains valid until end of trial)

Visit 6 & DS6: 12-month visit (week 52)

- Obtain medical and medication history since last visits
- Conduct Medication Adherence Rating Scale (for antipsychotic medication)
- Risk assessment using the Columbia Suicide Severity Rating scale
- Conduct clinical interviews (PANSS, CGI-SCH, CDSS, YMRS, MOAS, SWEMBS, SF-36, CSRI, UKU)
- Record weight
- Record vital signs (blood pressure/pulse rate)
- Collect blood sample for clinical laboratory assessments (full blood count, liver function test)
- Collect blood samples for pharmacogenomics, epigenetics and drug levels (antipsychotic and valproate)

- Remind female participants to continue to use effective long-term methods of contraception during the study

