10.3 Analysis

Statistical analysis will be done according to the predefined statistical analytical plan (SAP). There is no planned interim analysis unless the DMEC direct us to conduct one. Any deviations will be reviewed by the trial steering committee.

Statistical analysis

The primary analysis will use intention-to-treat principles by including all participants with outcome data in the arms to which they were randomized and follow the CONSORT 2010 statement. Baseline data will be presented using summary statistics with no testing for baseline differences. Treatment effects on the primary and secondary continuous outcomes will be estimated using linear mixed models fitted to outcome variables at all-time points. Fixed effects will be: diagnosis (schizophrenia/ schizoaffective); centre; baseline PANSS psychotic symptom severity rating; treatment; time (categorical); and time*treatment interactions. Marginal treatment effects will be estimated for outcomes at each time point and reported separately as adjusted mean differences in scores between the randomised groups with 95% confidence intervals and two-sided p-values. For binary outcomes, the same approach will be followed using logistic mixed models. All models will be estimated using maximum likelihood estimation, which allows for missing outcome data under the Missing At Random assumption. We may also use inverse probability weighting or multiple imputation to adjust for non-adherence to allocated treatment and other intermediate outcomes as predictors of future loss to follow-up.

Secondary analysis will include accounting for treatment switches from placebo to valproate arms using inverse probability of censoring weighting to estimate the average

treatment effect and longitudinal instrumental variable analysis to estimate the complier average causal effect.

Cost effectiveness evaluation

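### Section 6.5 delays outcome assessments for a study-drug holiday without limit, so the primary outcome can fall outside its week-52 window

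*Protocol*

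**What the plan says.** Protocol Section 6.5 (Withdrawal of Subjects): "Study drug holiday is permissible in case of an emergency, or for elective surgery or medical procedures". Study drug is tapered to zero as in Section 4.3 and titrated up again when the patient returns. The rule on visits follows: "In such cases their assessments will be delayed depending on the study drug holiday period". No maximum is given for the holiday or the delay, and the section does not say whether the holiday period counts only days fully off drug or also the down- and up-titration.

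Other sections fix the clock:

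- Section 4.1.1 gives the primary outcome as "Superiority of valproate compared to placebo on the Positive and Negative Syndrome Scale (PANSS) positive subscale at the 12-month visit".
- Section 7.1 places Visit 6, the 12-month visit, at week 52. The flow diagram in Section 4.2 marks randomisation as time zero.
- Section 4.3 sets the window: "study visits V4, V5 and V6 can take place within +/- 2 weeks of the specified week". It makes no exception for holidays. It adds that visits should be kept close to schedule and that a large departure will be taken into account in the analysis, without saying how.
- Section 6.6 keeps each subject on the active trial for 12 months, give or take two weeks for stopping treatment.
- Section 10.3 fits a linear mixed model with time as a categorical factor.

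For patients who stop study drug, Section 4.2 says: "All subjects will receive follow-up assessments, including those who discontinue the study medication". It mentions no delay.

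**The concern.** The sections give sites two incompatible instructions. A patient whose pause lasts more than two weeks cannot have assessments delayed by the length of the pause and also be seen inside the Visit 4 to Visit 6 windows.

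The statistical issue is that the date of the primary rating would be set by something that happens to the patient's treatment after randomisation. The trial compares the arms at a fixed time. If patients who pause are rated later, part of the sample is measured at a different elapsed time, and that part is selected by events during follow-up. The model in Section 10.3 uses the visit label and not the elapsed time, so a rating at week 56 or 60 enters as a 12-month value unless something further is specified. The same applies to the 3-month PANSS positive score, the main secondary outcome, where a given delay is a larger share of the interval.

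**Working it through.** No sample-size figure is in dispute; the check concerns dates.

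**Inputs.** Visit 6 at week 52 and Visit 4 at week 13 (Section 7.1); window of 2 weeks either side (Section 4.3); taper of 500 mg every 3–4 days (Section 4.3, applied to a holiday by Section 6.5); up-titration and tablets per day from day 16 onwards (Appendix 1). Holiday length is not given, so a range is shown.

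**Step 1, the planned window.** 52 − 2 = 50 and 52 + 2 = 54, so Visit 6 falls in weeks 50–54.

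**Step 2, Visit 6 after a delay of d days.** Week of visit = 52 + d/7.

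| Delay (days) | Visit 6 at week | In window? |
|---|---|---|
| 7 | 53 | yes |
| 14 | 54 | yes, at the edge |
| 28 | 56 | no |
| 56 | 60 | no |
| 84 | 64 | no |

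The conflict begins when d exceeds 14. For Visit 4, a 28-day delay gives week 13 + 4 = 17 against a window of 11–15; 4/13 is about 31% of the planned interval.

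**Step 3, if the holiday period includes titration.** Let t be the tablets per day from day 16 onwards. The taper takes between (t − 1) × 3 days (first cut on day 0, 3-day intervals) and t × 4 days (every step held 4 days). Re-titration is the number of days before Appendix 1 reaches t tablets. With no day fully off drug:

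| Weight (kg) | t | Taper (days) | Re-titration (days) | Total (days) |
|---|---|---|---|---|
| 35–49 | 2 | 3–8 | 6 | 9–14 |
| 50–99 | 3 | 6–12 | 12 | 18–24 |
| 100–134 | 4 | 9–16 | 12 | 21–28 |
| over 134 | 5 | 12–20 | 15 | 27–35 |

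Every band but the lightest exceeds 14 days. The upper taper values for 4 and 5 tablets run past the two weeks or so that Section 4.3 describes. Capping the taper at 14 days gives upper totals of 14 + 12 = 26 and 14 + 15 = 29, so the conclusion does not change. An abrupt stop in an emergency would remove the taper term and leave 6, 12, 12 and 15 days. At 3 or 4 tablets that leaves 14 − 12 = 2 days of margin for time off drug.

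**Step 4, what the analysis can do.** Section 4.3 undertakes to account for large departures. Using actual dates could adjust for a late rating, but Section 10.3 as written uses categorical time, and no adjustment supplies a week-52 rating that was not taken.

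**Step 5, how many patients.** This cannot be computed. The protocol gives neither a frequency nor a typical length for holidays.

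**The case against.** The strongest reply is that the protocol foresees the problem: Section 4.3 says large timing departures will be dealt with in the analysis, and the method belongs in the SAP, which is not shown. That is a fair answer to a complaint about missing analysis detail. It does not answer this point, because Section 6.5 is a rule for collecting data: it tells sites to rate late.

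The rule can also be read narrowly, as postponing only a visit that falls during the holiday. A pause in month 4 would then leave Visit 6 at week 52. The wording permits this, and it would reduce the number of late visits. The conflict would remain for any pause that overlaps a visit window, and the text does not say which reading is meant.

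There are practical reasons too. A PANSS interview may be impossible during an emergency admission, and a late rating is usually better than none. This stands, and the fix allows for it.

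A reader might draw stronger conclusions that the documents do not support:

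- *That the rule breaches intention to treat.* Section 10.3 defines it by arm: "The primary analysis will use intention-to-treat principles by including all participants with outcome data in the arms to which they were randomized". A patient rated late is still analysed in that arm.
- *That the delay is meant to restore exposure, or will differ between arms.* No such purpose is stated, the trial is double-blind, and nothing in the text predicts an imbalance.
- *That patients who stop for good are certainly rated on time.* Section 4.2 mentions no delay for them, but does not state their timing; the contrast is inferred.
- *That late recruits could run past the end of the trial.* Section 6.6 ties the end to the last patient's Visit 7, which would move with the delay.
- *That the QALY and cost period is lengthened.* Area under the curve can be cut at 12 months using actual dates, and a service-use recall of fixed length is shifted by a late visit, not lengthened.

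**Conclusion.** The point holds as a conflict between Section 6.5 and the visit timing in Sections 4.1.1, 4.3, 6.6 and 7.1. It arises for any delay over 14 days; shorter delays stay in the window and do no harm. Where it arises, the timing of the primary outcome depends on a treatment event after randomisation, which weakens the comparison at a fixed 12 months.

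The size rests on assumptions that the protocol leaves open: how long holidays last, whether titration counts, and whether the whole schedule shifts or only the visit concerned. Visit 6 falls at week 56 for a 4-week delay and week 60 for an 8-week delay. If holidays are rare, the effect on the treatment estimate is probably small, and its direction cannot be predicted. The correction is still worth making, because it is cheap and a rating missed at week 52 cannot be recovered later. The planned sample size is unaffected. Whether and how a holiday is taken is a clinical matter and is not judged here.

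**What to change.** Reconcile Sections 4.3, 6.5 and 10.3 by replacing the delay sentence in Section 6.5 with:

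*Outcome assessments (PANSS and the other 3-, 6- and 12-month measures) remain timed from randomisation (+/-2 weeks) irrespective of any study-drug holiday; if a visit cannot be held in the window it is held as soon as possible and its actual date, and the holiday dates, are recorded.*

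Leave the holiday, titration and dispensing arrangements as they are. With actual dates recorded, the SAP can state how any remaining out-of-window ratings are used.

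The cost is small but not nil. Some assessments will fall during or just after a pause. Visits 4 to 6 are also dispensing visits, and Visit 6 starts the final taper, so an assessment may sometimes have to be held separately from those steps.

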7.1 By Visit

ATLANTIS study visits

Visit 1: Face-to-face consenting and screening visit (approximately -8 to 0 weeks)

Following a telephonic or face-to-face conversation and provision of information on the study, subjects will be invited for consenting and screening. A unique screening number will be assigned to each subject.

Subjects will be evaluated during the face-to-face screening visit to determine their eligibility to enrol in the study after obtaining their consent.

The following procedures will be performed at Screening:

- Explain study procedures
- Obtain signed informed consent, capacity assessment and privacy authorization from the subject before conducting any other visit procedures
- Collect demographic information
- Review inclusion and exclusion criteria (conduct clinical interview using SCID-5 and PANSS)
- Conduct frailty assessment if needed
- Record medical and psychiatric history
- Record current and past medication use
- Conduct Medication Adherence Rating Scale (for antipsychotic medication)
- Conduct Risk assessment using the Columbia Suicide Severity Rating scale
- Record vital signs (blood pressure/pulse rate)
- Record height and weight

- Collect blood sample for clinical laboratory assessments (full blood count, liver function test if needed based on medical history)
- For female subjects, collect serum/ urine samples for pregnancy tests
- For female subjects of childbearing potential, review their current choice of contraception
- Complete the pregnancy annual risk Acknowledgement form for female subjects
 of childbearing potential if not completed yet (if serum pregnancy test needs to
 be done then conduct one)
- Collect blood samples for pharmacogenomics, epigenetics, antipsychotic drug levels

Visit 2 & DS1: Day 1: Baseline measures and Valproate titration begins (week 0)

- Review inclusion and exclusion criteria
- Review recent medical and medication history for changes since screening visit
- Conduct Medication Adherence Rating Scale (for antipsychotic medication)
- Risk assessment using the Columbia Suicide Severity Rating scale (baseline assessment)
- Conduct clinical interviews/assessments (PANSS, CGI-SCH, CDSS, YMRS, MOAS, SWEMBS, SF-36, CSRI, UKU)
- Record weight
- Record vital signs (blood pressure/pulse rate)
- Collect blood samples for pharmacogenomics, epigenetics, antipsychotic drug levels and other measures before IMP ingestion if not collected earlier
- Ensure female participants use effective long-term methods of contraception during the course of the study
- Explain the drug titration process
- Randomise the patient
- Dispense 2 weeks of medication (completed annual risk acknowledgment form will be needed for female subjects of childbearing potential prior to dispensing)
- Follow up after one week (via telephone/face to face) to check on how the
 patient is progressing with drug titration and also check if there are any concerns

Visit 3 & DS2: Face-to-face 2-week visit (week 2)

- Review recent medical and medication history for changes since previous visit
- Record vital signs (blood pressure/pulse rate)
- Remind female participants to continue to use effective long-term methods of contraception during the study

- If there is a gap in contraception or if the contraceptive method has been changed then conduct a urine pregnancy test before dispensing study medication
- Conduct Medication Adherence Rating Scale (for antipsychotic medication)
- Conduct a pill count of the IMP
- Dispense 3 months of medication (check if completed annual risk acknowledgment form for female subjects of childbearing potential remains valid)
- Where the target dose has not been reached, and where an increase in dose is executed at this visit then a telephone call/face-to-face visit to check on tolerability to be conducted after approximately three days.

Visit 4 & DS3: 3-month visit (week 13)

- Obtain medical and medication history since the last visit
- Conduct Medication Adherence Rating Scale (for antipsychotic medication)
- Risk assessment using the Columbia Suicide Severity Rating scale
- Conduct clinical interviews (PANSS, CGI-SCH, CDSS, YMRS, MOAS, SWEMBS, SF-36, CSRI, UKU)
- Record weight
- Record vital signs (blood pressure/pulse rate)
- Collect blood sample for clinical laboratory assessments (full blood count, liver function test)
- Collect blood samples for pharmacogenomics, epigenetics and drug levels (antipsychotic and valproate) and other measures
- Remind female participants to continue to use effective long-term methods of contraception during the study
- If there is a gap in contraception or if the contraceptive method has been changed then conduct a urine pregnancy test before dispensing study medication
- Conduct a pill count of the IMP
- Dispense 3 months of medication (check if completed annual risk acknowledgment form for female subjects of childbearing potential remains valid)
- If an increase in dose is executed at this visit then a telephone call to check on tolerability to be conducted after three days

Visit 5 & DS4: 6-month visit (week 26)

- Obtain medical and medication history since last visit
- Conduct Medication Adherence Rating Scale (for antipsychotic medication)

- Risk assessment using the Columbia Suicide Severity Rating scale
- Conduct clinical interviews (PANSS, CGI-SCH, CDSS, YMRS, MOAS, SWEMBS, SF-36, CSRI, UKU)
- Record height and weight
- Record vital signs (blood pressure/pulse rate)
- Remind female participants to continue to use effective long-term methods of contraception during the study
- If there is a gap in contraception or if the contraceptive method has been changed then conduct a urine pregnancy test before dispensing study medication
- Conduct a pill count of the IMP
- Dispense 3 months of medication (check if completed annual risk acknowledgment form for female subjects of childbearing potential remains valid at this time-point but also if it lasts till the end of medication phase and if needed perform a serum pregnancy test and complete a fresh annual risk acknowledgement form)

DS 5: 9-month dispensing session (week 36)

- Remind female participants to continue to use effective long-term methods of contraception during the study
- If there is a gap in contraception or if the contraceptive method has been changed then conduct a urine pregnancy test before dispensing study medication
- Conduct a pill count of the IMP
- Dispense 3 months of medication (check if annual risk acknowledgment form for female subjects of childbearing potential remains valid until end of trial)

Visit 6 & DS6: 12-month visit (week 52)

- Obtain medical and medication history since last visits
- Conduct Medication Adherence Rating Scale (for antipsychotic medication)
- Risk assessment using the Columbia Suicide Severity Rating scale
- Conduct clinical interviews (PANSS, CGI-SCH, CDSS, YMRS, MOAS, SWEMBS, SF-36, CSRI, UKU)
- Record weight
- Record vital signs (blood pressure/pulse rate)
- Collect blood sample for clinical laboratory assessments (full blood count, liver function test)
- Collect blood samples for pharmacogenomics, epigenetics and drug levels (antipsychotic and valproate)

- Remind female participants to continue to use effective long-term methods of contraception during the study
- If there is a gap in contraception or if the contraceptive method has been changed then conduct a urine pregnancy test before dispensing study medication
- For female subjects, collect serum/ urine samples for pregnancy tests
- Conduct a pill count of the IMP
- Dispense medication if needed (check if completed annual risk acknowledgment form for female subjects of childbearing potential is valid till the down-titration is completed irrespective of whether medication is dispensed)
- Explain down titration and advise subject to carry out in steps of 500mg in 3 to 4 days intervals.
- Liase with patient's clinical team to ensure smooth transition after completion of study

Visit 7: End of study (week 54)

- Record vital signs (blood pressure/pulse rate)
- Complete PANSS and UKU
- Conduct a pill count of the IMP
- Collect all unused study medication
- Remind female subjects of childbearing potential to continue using effective long-term methods of contraception until 60 days since their last study drug intake
- If there is a gap in contraception or if the contraceptive method has been changed then conduct a urine pregnancy test
- Complete the exit interview
- A single follow up either face-to-to face or via telephone 60 days since their last study drug intake to record for any AEs/SAEs

Post 1-year (annual)

- Record the HoNOS score
- Record the clinical inputs received by the patient since last assessment (hospitalisation, crisis/home treatment use, relapse & remission phases and medication use including valproate and switch to clozapine)

Early exit (if the patient consents)

Steps in Visit 6 and Visit 7 to be followed

Participants will be compensated for their time or a pro rata basis When participants discontinue their medication but not withdraw from the study, this payment will still be made for assessments.

